#### 5. Protein markers via tampon recovery before and after treatment:

Perform pre- and post-treatment proteomic analysis of vaginal proteins from tampon recovery to identify biomarkers that may predict response to exemestane treatment.

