### **8.2.4 DNA mutational analysis through Next Generation Sequencing and methylation status of endometrial tumor and vaginal DNA:**

Analyze DNA from the CAH/EIN or low grade endometrial carcinoma for specific genetic mutations, microsatellite instability and hypermethylation in order to correlate exemestane response to mutational status. Additionally, vaginal DNA (recovered from tampon collection) will be analyzed for presence of tumor mutations or hypermethylation.

**8.2.4.1 Tumor genetics:** As evident by the recent TCGA analysis of >350 endometrial carcinomas, endometrioid tumors have frequent mutations in a variety of genes including PTEN, CTNNB1, PIK3CA, KRAS, and POLE. Furthermore, the TCGA categorized endometrial carcinoma into 4 prognostically significant groups characterized by; 1) POLE hotspot mutations and endometrioid morphology; 2) microsatellite instable (MSI) tumors with mutated PTEN and endometrioid morphology; 3) microsatellite

stable (MSS) tumors with mutated PTEN and endometrioid morphology; and 4) MSS tumors with mutated TP53, high somatic copy number alteration burden and predominantly serous or mixed morphology. We hypothesize that response to exemestane may correlate with tumor genetics and these described subtypes. We therefore seek to determine the mutational status of all tumors with DNA panel testing to see if this correlates with treatment response. In this context, tumor response will be defined as any decrease in absolute Ki-67 expression by  $\geq 5\%$ .

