We anticipate that the samples will contain varying amounts of blood, so we will use commercially available platforms that were specifically designed to be used with serum or plasma samples. There are currently two major companies that have products that would be amenable to the identification of protein biomarkers in serum samples: Olink and SomaLogic. Olink technology was initially designed to quantify the levels of proteins in sera and/or plasma using Proximity Extension Assays. (See their website at <https://www.olink.com/>) Thus, the Olink platform is well suited to handle the endometrial samples, which contain high amounts of blood proteins. The unique technology behind the Olink® Target 96 panels enables high-throughput, multiplex immunoassays that measure 92 proteins across 96 samples simultaneously using only one microliter of serum, or plasma. The Olink panels have also been used on other type of biological samples. We have searched their lists of more than 1500 proteins that they can measure in their 13 commercially available “Target 96” panels. We found >100 proteins that fall into the category of “proliferation” (which is the focus of this project) on five of their panels. Since each panel measures 92 proteins, this will result in generating data for the levels of  $92 \times 5 = 460$  proteins. This is far better than we could expect from MS experiments that are contaminated with blood proteins.

We propose to: 1-Determine the feasibility of using the Olink panels by running one panel (Immuno-Oncology) to analyze the tampon washing samples, since we are not certain of the dilution of protein that will yield optimal results. We will extract protein from the 20 tampon washing cell pellets and use various dilutions of the tampon washing cell pellet lysates and supernatants. We will place aliquots of the diluted samples into a 96-well microtiter plate from the 40 tampon washing samples (10 pre-treatment supernatants, 10 post-treatment supernatants, 10 pre-treatment cell pellets, and 10 post-treatment cell

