### 13.4 Primary Objective, Endpoint(s), Analysis Plan

The primary objective is to determine if there is a decrease in proliferation index, measured by percent Ki-67 expression, in CAH/EIN or low grade endometrial cancer cells from baseline to post-exposure. Therefore, the primary endpoint is the absolute change in Ki-67 expression in endometrial cancer cells from baseline to post-exposure. We will evaluate the change from baseline to post-exposure in absolute change in Ki-67 using one-sample Student's t-test or Wilcoxon signed-rank test, as appropriate. In addition, we will evaluate the change relative to the change recorded in the historic cohort.

Ki-67 values for patients with endometrial cancer are available in prior research. When the patients from this paper are limited to those with low grade cancers, the mean (standard deviation) of the decrease from baseline was 7.2 (7.5) among the treated patients. Given an SD of 7.5, the table below shows the detectable effect sizes (defined as the mean change divided by the standard deviation of the change) and mean changes for a one-sided test for significance level  $\alpha=0.05$  and various power ( $1-\beta$ ) levels for the primary endpoint given the effective sample size of 30. For example, using an 0.05 level one-sided one-sample Student t-test, we would be able to detect an effect size of 0.50, which corresponds to a mean decrease of 3.8, with 0.85 power.

	Power		
	0.80	0.85	0.90
Effect Size	0.46	0.50	0.55
Mean Decrease	3.5	3.8	4.1

The mean decreases in this table are smaller than the mean difference in the treatment group for those with low grade endometrial cancer in the prior research with letrozole. We are including CAH/EIN in addition to low grade endometrial cancer in the current study and therefore it is not unreasonable to expect a lesser treatment effect for these patients with a less severe form of the disease. For these reasons, we feel there is a need to power for smaller differences.

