### 13.5 Secondary Objectives, Endpoints, Analysis Plans

The secondary objectives are to examine and test change in circulating serum estradiol and progesterone, histology, and tissue biomarkers. Additionally, we will correlate response with tumor DNA mutations, and

protein and DNA markers via tampon recovery. Therefore, the secondary endpoints are the changes in circulating serum estradiol and progesterone levels, in tissue biomarkers such as apoptosis as measured by cleaved caspase 3 level, proliferation as measured by cyclin D1 level, and insulin pathway as measured by pAKT and IGF-1R levels, and hormone receptor changes as measured by ER, PR and AR.

All tumors will be sequenced via Next Generation Sequencing panel testing and also be tested for microsatellite instability. Results of tumor genetic testing will be correlated with exemestane response as defined by the change in Ki-67 expression.

As an exploratory endpoint, we will attempt to identify the genetic mutation of the primary tumor by performing Next Generation Sequencing of tampon collected DNA. Additionally, vaginal proteomic analysis will also be performed via tampon collection and correlated with tumor response to exemestane as defined by the change in Ki-67 expression.

To evaluate the reliability of methylation measurement assayed on the 850K EPIC chip, an intraclass correlation coefficient (ICC) will be calculated for each CpG site using the technical replicates (using 4 blinded duplicate measurements). We aim to classify the CpG sites into multiple reliability groups, by modeling the distribution of ICC values using a mixture distribution.

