The degree of methylation will be determined using Illumina GenomeStudio software. The methylation score for each CpG will be represented as a beta ( $\beta$ ) value calculated by dividing the fluorescence intensity of the methylated allele by the sum of the intensities of the methylated allele and unmethylated allele.  $\beta$ -values may take any value between 0 (non-methylated) and 1 (completely methylated). Background subtraction will be conducted with the GenomeStudio software using built-in negative control bead types on the array. An average normalization will also be applied in GenomeStudio to minimize scanner-to-scanner variation using ~90 normalization probe pairs included on the array, which target housekeeping regions with no underlying CpG sites. These probes will be used to independently calculate normalization values in the green and red channels so that all samples have the same average intensity.

We will identify individual DNA methylation sites ( $\beta$  values as independent variables) in the 850K EPIC chip that are either overexpressed or underexpressed in endometrial tumor DNA by focusing on the tails of distribution of the  $\beta$  values. We will evaluate whether those individual methylation sites can be detected in the matched tampon DNA. We realize that this study is not powered to comprehensively identify all individual DNA methylation markers in endometrial cancer and will perform these analyses to potential targets that can be confirmed in future studies.

Vaginal and tumor DNA methylation studies will be performed; the signals from methylated (M) and unmethylated (U) bead types will be used to calculate  $\beta = M/(U + M)$  for the 850,000CpG sites that the EPIC methylation chip evaluates. Correlations will be tested between vaginal and tumor DNA methylation at each CpG site, adjusting for covariates, possibly including age. Linear mixed models adjusting for covariates such as age and histology (CAH/EIN vs grade 1/2) will be used to test for relationships between vaginal DNA methylation at CpG sites and the primary endpoint, change in Ki-67. A False Discovery Rate (FDR) q-value of 0.05 will be applied to adjust for multiplicity in these tests; where an FDR is not appropriate, a Bonferroni correction will be used.

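### Section 13.5 relates markers to absolute Ki-67 change without prespecifying baseline Ki-67, so a marker of starting proliferation can look like a predictor of response if the fall scales with the starting level

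*Combined protocol and SAP*

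**What the plan says.** **Outcome.** Section 13.4: "the primary endpoint is the absolute change in Ki-67 expression in endometrial cancer cells from baseline to post-exposure".

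**Mutations.** Section 13.5: "Results of tumor genetic testing will be correlated with exemestane response as defined by the change in Ki-67 expression". No model or covariate is given. Section 8.2.4.1 adds a binary version for this analysis: "tumor response will be defined as any decrease in absolute Ki-67 expression by" at least 5%, whatever the starting value.

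**Vaginal methylation.** Section 13.5: "Linear mixed models adjusting for covariates such as age and histology (CAH/EIN vs grade 1/2) will be used to test for relationships". The outcome in these models is the Ki-67 change, and the marker is the methylation level at each site. Multiplicity is handled by an FDR q-value of 0.05, or Bonferroni where FDR does not suit.

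**Tampon proteins.** Section 13.5 says these are "correlated with tumor response to exemestane as defined by the change in Ki-67 expression", again with no covariate. Section 8.2.5 also compares proteins between responders and non-responders, and allows the second proteomic stage to be limited to responders.

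**Purpose.** Secondary Objective 5 (Section 1.2) is "to identify biomarkers that may predict response to exemestane treatment".

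Nowhere do the documents name baseline Ki-67 as a covariate, use relative or log change, or model post-treatment Ki-67 given baseline. The historical cohort (Sections 8.2.7 and 13.2) gives context for the overall change and is not linked to the marker analyses.

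**The concern.** An absolute fall can depend on where a woman starts. The same 25% relative fall is 3 points from a Ki-67 of 12% and 10 points from 40%. Under the responder rule, a woman who starts below 5% cannot respond at all. With a uniform 24% fall, only women who start above 5/0.24 = 20.8% reach 5 points, apart from noise.

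If the drug acts roughly proportionally, a marker of how fast the lesion was dividing at entry will therefore correlate with the fall, even when no woman is proportionally more sensitive than another. The protein work makes this concrete. The Olink panels were picked with proliferation in mind: "We found >100 proteins that fall into the category of" proliferation, on five panels.

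FDR and Bonferroni control chance findings. They do not guard against an association that is real but reflects baseline. At stake is which candidates go forward for confirmation as predictors of exemestane response.

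**Working it through.** **1. The plan's own figure.** Section 13.4: one-sided one-sample t-test, alpha 0.05, n = 30, effect size 0.50. The noncentrality is 0.50 × √30 = 2.74 on 29 degrees of freedom, which gives power 0.848 against the stated 0.85. The design figure reproduces, and nothing below affects it. The plan gives no figure for the marker analyses.

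**2. Inputs.**
- From the documents: n = 30 evaluable (Section 13.1), mean fall 7.2 and SD of the fall 7.5 (Section 13.4, from the cited letrozole study), and a 10-patient proteomic pilot (Section 8.2.5).
- Assumed, because the documents do not give them: baseline mean 30%; baseline SD 10, 15 or 20; the same 24% fall in every woman (0.24 × 30 = 7.2); correlation ρ of 0.5 or 0.7 between marker and true baseline.

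**3. Model.** True baseline is T, measured baseline B = T + e1, and post-treatment P = 0.76T + e2. The fall is D = B − P = 0.24T + e1 − e2, with error scaled so that SD(D) = 7.5. The marker M is related to T only. Then

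corr(D, M) = r = ρ × 0.24 × SD(T) / 7.5.

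The chance of two-sided p < 0.05 is approximately Φ(z − 1.96) + Φ(−z − 1.96), with z = atanh(r) × √(n − 3).

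**4. Results without baseline Ki-67, n = 30** (simulation: 20,000 trials per cell)

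| Baseline SD | ρ | r | Formula | Simulation |
|---|---|---|---|---|
| 10 | 0.5 | 0.160 | 13.4% | 13% |
| 10 | 0.7 | 0.224 | 22.0% | 22% |
| 15 | 0.5 | 0.240 | 24.6% | 25% |
| 15 | 0.7 | 0.336 | 44.3% | 46% |
| 20 | 0.5 | 0.320 | 40.7% | 42% |
| 20 | 0.7 | 0.448 | 70.7% | 72% |

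SD 20 is an extreme case: a normal distribution with mean 30 and SD 20 puts 6.7% of women below zero.

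**5. Ten-patient pilot.** The same calculation with n = 10 gives about 7–10% at SD 10 and 10–16% at SD 15.

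**6. If the fall does not depend on baseline.** With a constant 7.2-point fall, the unadjusted test flags the marker in 5% of trials. Adjusting for the error-prone measured baseline raises this to 11% (ρ = 0.5) or 20% (ρ = 0.7).

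**7. Proportional fall, baseline Ki-67 in the model, n = 30.**
- Error split equally between B and P: 11–22% at SD 10, 8–13% at SD 15, 6–9% at SD 20.
- All error in B: 13–80% across the same cases.
- All error in P: about 5%.

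Adjustment helps clearly when baseline is well measured, and can mislead when it is not.

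**8. Requiring both analyses to be significant.** This brings false flags to about 1–3%, or 12–14% with all error in B and ρ = 0.7. It is costly. For a genuine marker effect of 3 points per marker SD (baseline SD 15, error split equally), detection falls from about 90% unadjusted to about 45% if the marker correlates +0.5 with baseline, and from about 80% adjusted to about 14% if it correlates −0.5.

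**The case against.** Several points on the other side stand.

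- **The covariate list is open.** Age and histology are examples. Baseline Ki-67 is unspecified, not excluded, and the sentence covers vaginal methylation only. With n = 30 and very many tests, this still leaves a consequential choice to be made after the data are seen.
- **The plan chose absolute change.** A marker of larger absolute falls does predict response as the plan defines it. Calling it a false flag assumes that relative sensitivity is what matters, and the documents do not say so. The objection does not settle how such a marker should be described to whoever plans the next study.
- **The rates are not those of the planned tests.** They are per test at 0.05. Methylation uses FDR or Bonferroni and adjusts for histology, which may absorb part of the baseline difference. At 0.05/850,000, the SD 15, ρ = 0.7 case is flagged in only about 0.003% of trials. Binary mutation status and the 5% responder rule were not simulated.
- **The protein premise is partial.** The proliferation proteins are a little over 100 of 460 Olink measurements, the first panel is Immuno-Oncology, and SomaLogic measures 7000 proteins. Tampon washings also carry cervical, vaginal and blood proteins. No document supports a correlation of 0.5 to 0.7 with lesion Ki-67.
- **The work is exploratory.** Sections 8.2.5, 13.4 and 13.5 say so in different ways.

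These points limit the size and reach of the concern. None of them supplies a baseline-adjusted analysis.

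**Conclusion.** The gap is real and worth closing before analysis. All three marker-response analyses use absolute Ki-67 change, and baseline Ki-67 is prespecified in none. If the fall is roughly proportional to starting Ki-67, a marker of starting proliferation is flagged in about 13–72% of trials at n = 30 and about 7–16% in the 10-patient pilot (SD 10 to 15), against a nominal 5%. These figures rest on the assumed 24% uniform fall, baseline mean and SD, and marker correlation.

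A reader might infer three stronger things that the documents do not support:
- That any marker of starting proliferation will pass as a predictor. If the fall is unrelated to baseline, a marker of true baseline is not inflated.
- That these percentages are the methylation error rates. They are not adjusted for FDR.
- That a marker should count only if it is significant both with and without baseline. Step 8 shows that this discards many genuine markers, a poor trade in a discovery study.

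**What to change.** Add to Section 13.5, with a cross-reference from Section 8.2.4.1:

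*Every analysis relating mutations, methylation or tampon proteins to Ki-67 response, including the 5% responder analysis, will be reported both as planned and with baseline Ki-67 in the model (post-treatment Ki-67 regressed on baseline Ki-67, histology and the marker). An association present only without baseline Ki-67 will be described as possibly reflecting starting proliferation. One present only with baseline Ki-67 will be described as possibly reflecting baseline measurement error. Agreement of the two analyses is not required for a candidate to be carried forward.*

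**Cost.** No new samples, visits or participants: baseline Ki-67 is already measured in every evaluable woman. Baseline uses one degree of freedom. With intercept, histology and marker, the residual goes from 27 to 26 at n = 30, and from 7 to 6 in the 10-patient pilot. There is a little more analysis work, and some candidates will carry a more cautious label. The primary one-sample test and the sample size do not change.

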### 13.6 Reporting and Exclusions

As noted above, we anticipate that approximately 25% of patients will not have CAH/EIN or low grade endometrial carcinoma on central pathology review or their tissue samples will not be adequate for measuring Ki-67 expression, thus making them unevaluable for final analysis. This will result in 30 evaluable patients, the effective sample size for the study. These cases will be considered random loss, and will be excluded from analysis. Otherwise, all cases will be included in the analysis regardless of

compliance with the protocol treatment. All cases that received any amount of exemestane will be included in the analysis of toxicity as indicated below.

### **13.7 Evaluation of Toxicity**

All participants will be evaluable for toxicity from the time of their first dose of exemestane using CTCAE version 4.0. The incidence and severity of adverse events will be summarized with frequency and proportion.

### **13.8 Evaluation of Response**

Pathological response, i.e. regression of endometrial hyperplasia and carcinoma in pre-treatment biopsies to final surgical tissue samples, will be summarized with frequency and proportion. All of the participants who met the eligibility criteria, with the exception of those who did not receive study agent, will be included in the main analysis. Random dropouts will be excluded. Data will be examined for non-random dropouts. An appropriate sensitivity analysis will be conducted in the case of missing data.

### **13.9 Interim Analysis**

There is no planned interim analysis of the primary endpoint of the study. Safety data will be monitored periodically by the consortium's data and safety monitoring committee.

### **13.10 Ancillary Studies**

Not Applicable

## **14. ETHICAL AND REGULATORY CONSIDERATIONS**

### **14.1 Form FDA 1572**

Prior to initiating this study, the Protocol Lead Investigator at the Lead or Participating Organization(s) will provide a signed Form FDA 1572 stating that the study will be conducted in compliance with regulations for clinical investigations and listing the investigators, at each site that will participate in the protocol. All personnel directly involved in the performance of procedures required by the protocol and the collection of data should be listed on Form FDA 1572.

### **14.2 Other Required Documents**

14.2.1 Current (within two years) CV or biosketch for all study personnel listed on the Form FDA 1572 and Delegation of Tasks form for the Lead Organization and all Participating Organizations.

14.2.2 Current medical licenses (where applicable) for all study personnel listed on Form FDA 1572 and Delegation of Tasks form for the Lead Organization and all Participating Organizations.

14.2.3 Lab certification (e.g., CLIA, CAP) and lab normal ranges for all labs listed on Form FDA 1572 for the Lead Organization and all Participating Organizations.

14.2.4 Documentation of training in "Protection of Human Research Subjects" for all study personnel listed on the FDA Form 1572 and Delegation of Tasks form for the Lead Organization and all Participating Organizations.

14.2.5 Documentation of Federalwide Assurance (FWA) number for the Lead Organization and all Participating Organizations.

14.2.6 Signed Investigator's Brochure/Package Insert acknowledgement form

14.2.7 Delegation of Tasks form for the Lead Organization and all Participating Organizations signed by the Principal Investigator for each site and initialed by all study personnel listed on the form

14.2.8 Signed and dated NCI, DCP Financial Disclosure Form for all study personnel listed on Form FDA 1572 for the Lead Organization and all Participating Organizations

### **14.3 Institutional Review Board Approval**

Prior to initiating the study and receiving agent, the Investigators at the Lead Organization and the Participating Organization(s) must obtain written approval to conduct the study from the CIRB. Should changes to the study become necessary, protocol amendments will be submitted to the DCP PIO according to DCP Amendment Guidelines. The DCP-approved amended protocol must be approved by the CIRB prior to implementation

### **14.4 Informed Consent**

All potential study participants will be given a copy of the IRB-approved Informed Consent to review. The investigator will explain all aspects of the study in lay language and answer all questions regarding the study. If the participant decides to participate in the study, he/she will be asked to sign and date the Informed Consent document. The study agent(s) will not be released to a participant who has not signed the Informed Consent document. Subjects who refuse to participate or who withdraw from the study will be treated without prejudice.

Participants must be provided the option to allow the use of blood samples, other body fluids, and tissues obtained during testing, operative procedures, or other standard medical practices for further research purposes. If applicable, statement of this option may be included within the informed consent document or may be provided as an addendum to the consent. A Model Consent Form for Use of Tissue for Research is available through a link in the DCP website.

Prior to study initiation, the informed consent document must be reviewed and approved by NCI, DCP, the Consortium Lead Organization, and the IRB at each Organization at which the protocol will be implemented. Any subsequent changes to the informed consent must be approved by NCI, DCP, the Consortium Lead Organization's IRB, and then submitted to each organization's IRB for approval prior to initiation.

